Institute for Health and Society
Division of Biostatistics
[name]
[name]
[contact]
[contact]

PROTOCOL SUMMARY

[figure not shown]
Title	An Exploratory Study of Neoadjuvant Endocrine Therapy in Hormone Receptor-Positive HER2-negative Node-Negative Breast Cancer Patients to Assess Responses and Mechanisms of Endocrine Resistance
Protocol Number	FP00011093; PRO 30178.
IND Sponsor	N/A
Principal Investigator	[name], MS
Study Sites	St. Joseph's Hospital, West Bend Community Memorial Hospital, [name] Memorial Lutheran Hospital
Clinical Trial Phase	Exploratory
Study Disease	Hormone receptor-positive (HR+), HER2-negative (Her2-), node-negative pre and postmenopausal breast cancer patients.
Study Rationale	Patients with HR+ HER2- node-negative breast cancers generally undergo surgical resection upfront, followed by adjuvant chemotherapy, if needed, in addition to adjuvant endocrine therapy. Because endocrine therapy is primarily delivered in the postoperative setting, the ability to assess the tumor response to this treatment modality is lost and very difficult to assess. This study offers the unique opportunity to assess the responsiveness of breast tumors to endocrine therapy while the tumors are still in vivo by treating patients with endocrine therapy before surgery and assessing molecular changes with treatment. By comparing pre- and post-treatment levels of molecular markers in individual tumors, we expect to identify predictors of responsiveness to existing agents and identify new candidate therapeutic targets.
Primary Objectives	Our primary objective is to determine the frequency of increased HER family of receptor tyrosine kinases protein expression in tumors, following treatment with neoadjuvant endocrine therapy and their correlation with Ki-67 tumor responses. We will measure cancer cell protein levels of growth factor receptors of the HER family before and after neoadjuvant endocrine therapy. The data will be used to inform a future randomized trial of combined endocrine and the most promising anti-HER targeted therapy.
Secondary Objectives	
 - To determine changes in additional selected molecular markers (CK5+/ER- progenitor cells, PD-L1, PD-L2, BTK, iron-related proteins) and correlate with Ki-67 responsiveness to endocrine therapy in our pre- and post-treatment tumor specimens.

	
 - Assess changes in tumor size on radiographic images with neoadjuvant endocrine therapy and correlate with changes in biomarkers and Ki-67.
Endpoints	
Primary endpoints are:
 
 - Change in cancer cell protein levels of HER family members (HER1-4) with neoadjuvant endocrine therapy and association with Ki-67. We hypothesize that the expression of one or more HER proteins (HER1-4) will be upregulated in at least 50% of tumors after four weeks of neoadjuvant endocrine therapy and this upregulation will correlate with Ki-67 expressed in more than 10% of cancer cells. 
Secondary end points are:
 
 - Determine whether an increased proportion of therapy-resistant CK5+ progenitor cells are negatively correlated with Ki-67 response and tumor volume reduction, in response to neoadjuvant endocrine therapy. - Assess changes in the % expression of ER and PR in pre- and post-treatment breast cancer tumor specimens and their correlations with Ki-67 and radiographic responses. - Assess changes in BTK protein expression with neoadjuvant endocrine therapy and correlation with responses. - Changes in iron-related protein expression, i.e., transferrin, ferritin, ferroportin and ribonucleotide reductase with neoadjuvant endocrine therapy and correlation with responses. - Changes in PD-L1 and PD-L2 protein expression with neoadjuvant endocrine therapy and correlation with responses. - Assess changes in tumor size on radiographic images with neoadjuvant endocrine therapy and correlate with changes in biomarkers and Ki-67. 
Chart review planned at about five years from completion of study to assess patient outcomes, i.e., ipsilateral, contralateral or distant recurrences.

Study Design	Exploratory study.
Study Agent/ Intervention Description	This is an exploratory interventional study that initiates standard-of-care anti-estrogen treatment preoperatively for four weeks, +/- 1 week.
Number of Subjects	37
Subject Participation Duration	Patients to be treated C1D1 for four weeks +/- 1 week.

Duration of Follow up	Within 30 days after completion of study treatment
Long term Follow up	As standard of care, patients will be followed by oncology provider(s) at least annually from surgery (+/- 3 months). Cancer outcomes up to five years post-treatment will be collected by chart review.
Estimated Time to Complete Enrollment:	2 years
Statistical Methodology:	
We hypothesize that expression of one or more HER proteins (HER1-4) will be upregulated in at least 50% of tumors after four weeks of neoadjuvant endocrine therapy and this upregulation will correlate with Ki-67 expressed in more than 10% of cancer cells, as compared to upregulation in 30% or less of tumors without the therapy. The change in Ki-67 expression will be dichotomized, as a categorical variable with $\geq 10\%$ increase coded as high and $< 10\%$ coded as low.
 
 - For the primary outcome: An exact binomial one sample test of proportions will be used for to test the hypothesis that proportion of upregulated HER proteins will be at least 50% after therapy versus the null hypothesis that the proportion of upregulated HER proteins is not greater than 30%. - For analyzing - the differences in proportion of upregulated HER proteins between the high difference in Ki-67 and low difference in Ki-67 groups, two sample tests of proportions will be used. - Similarly, appropriate two sample tests will be used to test differences in biomarkers between the high difference in Ki-67 and low difference in Ki-67 groups. We will use the appropriate kind of regression instead of two sample tests, to test differences in biomarkers between the high difference in Ki-67 and low difference in Ki-67 groups if we need to adjust for covariates. - Additionally, regression analysis will also be done to evaluate the changes in the biomarkers and their association with patient specific covariates, such as age, race and other relevant predictors of interest. 
Radiographic responses will be assessed by WHO criteria. We will use logistic regression (and other generalized linear models as appropriate) to measure association between the response rates and patient specific covariates such as age, race and other relevant predictors of interest.

	
To achieve at least 80% power at significance level of 0.05, when testing the one sided one sample hypothesis that the proportion of tumors with HER protein upregulation with neoadjuvant endocrine therapy is at least 50% versus the null hypothesis that the proportion is no larger than 30%, the minimum number of patients required is 37.

Safety Assessments	
 - Given the short nature of the treatment regimen (3-5 weeks), and expected low grades of toxicity, it is considered highly unlikely that a large percentage of patients will experience adverse events (AEs) from the endocrine treatment. - Patients would be assessed at beginning and end of treatment with neoadjuvant endocrine therapy at their follow-up visit within 30 days after completion of study treatment. - This study will be reviewed by the Medical College of Wisconsin Cancer Center Data and Safety Monitoring Committee (MCWCC DSMC).

SCHEMA

STUDY CALENDAR

Period / Procedure	Screening ^{1,2}	Neoadjuvant Endocrine Therapy Treatment ⁹				Surgery	End of treatment visit ¹⁰	Annual Follow up ¹¹
Study Day/ Visit Day		Week 1 ²	Week 2	Week 3	Week 4			
Informed Consent	X							
Adverse Event Assessment	X						X	
Current Medications	X						X	
Treatment / Drug Administration								
Aromatase Inhibitor OR Tamoxifen		X	X	X	X			
Calendar Collection							X	
Imaging								
Unilateral diagnostic mammogram and ultrasound ³	X					X		
Clinical Procedures								
Physical Exam	X	X					X	
Vital Signs	X	X					X	
Medical History	X	X					X	
Performance Status	X	X					X	
Recurrence Status								X
Laboratory Procedures								
CBC w/ Diff ⁴	X							
Blood Chemistry ⁵	X							
Fasting Lipid Panel ⁶	X							
Pregnancy Test (HCG) ⁷	X							
Study Biomarkers ⁸	X					X		

1. A patient can be screened and have status of week one on the same day.
2. Screening procedures and drug administration to be done within 28 days of enrollment.

3. Unilateral diagnostic mammogram and ultrasound to be done within 60 days prior to enrollment and within 5 days prior to surgery.
4. Including CBC with differential and platelet count.
5. Including alkaline phosphatase, ALT/AST, total bilirubin, calcium, phosphorus, creatinine, potassium, sodium, chloride, and bicarbonate.
6. Fasting lipid panel to be done once at screening; lipid panel may be performed within the last 12 months.
 - o This project does not ask Froedtert to bill routine care costs to patient insurance but does ask Froedtert to invoice MCW for the following services:
 - Lipid panel if it needs to be repeated and not obtained as SOC prior to study participation consideration
7. For premenopausal women only.

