4. After the informed consent is obtained with the patient's signature, the eligibility process begins. If the patient is deemed eligible, then the patient can participate in any study related procedures.
5. Interested patients must meet with a medical oncologist prior to study entry to determine if Oncotype Dx testing is recommended. If recommended and the patient is amenable to the possibility of receiving chemotherapy, there must be adequate biopsy tissue for testing. If adequate tissue is not available for the Oncotype Dx testing, patients may undergo additional biopsies. If a patient plans to decline chemotherapy, regardless of a high Oncotype Dx results, and elects to forgo the test, they will still be eligible for enrollment. If the patient elects to undergo an additional biopsy, but no residual tumor is found, then, the patient is not eligible for the study.
6. The Oncotype Dx assay is obtained initially in order to know which patient would benefit from the addition of adjuvant chemotherapy after her surgery, so that all patients undergo the appropriate standard-of-care postsurgical treatment. Treatment with neoadjuvant endocrine therapy is likely to induce changes within tumor biology and Oncotype Dx assay done after surgery in this setting may not provide reliable results, and thus, will not be performed after surgery.
7. Once enrolled, patients would be treated with the current standard-of-care endocrine therapy. Choice of endocrine therapy (aromatase inhibitors or tamoxifen) would be decided by medical oncologist, following a review of the patient's medical history and menstrual status. The patient would be treated with

endocrine therapy in a neoadjuvant setting for four weeks (+/- 1 week), with dosing continuing until surgery (+/- 2 days).

8. Patient compliance would be monitored by providing a calendar sheet to the patients to log in their daily use of prescribed endocrine therapy (Appendix.1). This calendar sheet will be returned to our clinical trial staff upon completion of the four-week (+/- 1 week) period of neoadjuvant endocrine treatment.

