 - Partial Response (PR):** A 50% or greater decrease in the product of the bidimensional measurements of the lesion (total tumor size), based on a comparison between the measurements at baseline and after four weeks of treatment with neoadjuvant therapy.
 - No Change (NC):** A 50% decrease in total tumor size cannot be established nor has a 25% increase in the size of the lesion been demonstrated.
 - Progressive Disease (PD):** A 25% or greater increase in the total tumor size of the measurable lesions (calculated on the smallest diameter recorded over time).

V. STUDY ENTRY AND WITHDRAWAL; STUDY PROCEDURES

Required Preregistration Screening Tests and Procedures

The study-specific assessments are detailed in this section and are outlined in the study calendar. Screening assessments must be performed within 28 days prior to enrollment. Any results falling outside of the reference ranges may be repeated at the investigator's discretion. Treatment or visit delays for public holidays or weather conditions do not constitute a protocol violation.

A written, signed informed consent form (ICF) and a Health Insurance Portability and Accountability Act (HIPAA) authorization must be obtained before any study-specific assessments are initiated. A separate consent form for tissue banking of residual tumor specimens would be used. Signed copies of the study consent forms would be given to the subject. and a copy will be filed in the medical record. The original study consent will be kept on file with the study records.

All patients who are consented will be registered in OnCore®, the MCW Cancer Center clinical trial management system. The system is password protected and meets HIPAA requirements.

Registration Procedures

Registration and Monitoring of Patients

1. Patients will be screened for eligibility and registered by a certified research associate/certified research coordinator (CRC/CRA) in the Clinical Trials Office of the Froedtert & the Medical College of Wisconsin Clinical Cancer Center.
2. Patients will be registered in the institutional OnCore® web-based system under the CRA console.

3. Registration of patients and information regarding consenting, eligibility review, on-study status, treatment status and follow-up will be monitored, using the OnCore® calendar system.
4. Serious adverse events (SAEs) and protocol deviations will be reported through the OnCore® reporting system.

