5. Questions regarding OnCore systems and data reporting should be reported to OnCore® data management.
6. Questions regarding patient eligibility and registration procedures should be directed to the principal investigator, [name], MS ([contact], [contact], office [contact]).
7. Subject Withdrawal. Given the short nature of the treatment regimen (three to five weeks), and none or few low-grade toxicities are expected, it is not considered likely that a large percentage of patients will withdraw from the study, once endocrine treatment has begun. However, subjects have the right to withdraw from the study at any time. In the rare case that a patient withdraws from the protocol after the initiation of treatment, only the data collected up until the date of withdrawal will be used in analysis.
8. A subject may be withdrawn from the study, if she wishes to decline treatment on the study. Subjects may also be withdrawn if there is a violation of the protocol inclusion and exclusion criteria, as deemed relevant by the treating physician and the principal investigator. As these patients would be withdrawn prior to delivery of study-related treatment, they will then be replaced on the study and not counted toward the total accrual goal of 39 patients. Similarly, patients withdrawing for any other reason prior to delivery of treatment will be replaced on the study and not counted toward the total accrual goal.
9. Patients who withdraw from the study should be treated in accordance with normal standard of care. Follow-up will be per the discretion of the patient's treating physicians, but at a minimum be in accordance with NCCN guidelines.

Pretreatment Period

Screening Assessments

Once the informed consent is signed, proceed with the screening procedures and assessments which must be completed within 28 days of prior to enrollment.

- Physical examination
- Vital signs
- Complete medical history
- Performance status (ECOG, KPS, etc.) (Appendix.2)

- Adverse event assessment
- Current medications
- Blood chemistry assessment, including
 - Complete blood count (CBC) with differential and platelet count
 - Alkaline phosphatase, aspartate aminotransferase/alanine aminotransferase - (ALT/AST)
 - total bilirubin
 - calcium
 - phosphorus,
 - creatinine,
 - potassium,
 - sodium,
 - chloride,
 - bicarbonate,
 - fasting lipid panel (low-density lipoprotein [LDL], total cholesterol, triglycerides) - within the past 12 months.

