- Serum or urine pregnancy test for premenopausal women
- Specimen collection for Oncotype Dx and study biomarkers once enrolled.
- Unilateral diagnostic breast mammogram and ultrasound within 60 days of enrollment

Study Procedures during Treatment

Patients must have met eligibility criteria on Day 1 to be treated. The clinic visit can be the same for screening, eligibility assessment and if enrolled, to start treatment with endocrine therapy for week 1. Patient will get treatment for 4 weeks (+/-1 week) before their surgery. No additional clinic follow ups are planned during this period, however can be scheduled per discretion of treating physician.

Surgery

- Diagnostic mammogram and ultrasound are required within 5 days prior to surgery
- Surgical specimen collection for study biomarkers

End of Treatment Visit

The end of treatment visit would be scheduled within 30 days from surgery.

- Physical examination
- Vital signs

- Complete medical history
- Performance status (ECOG, KPS, etc.)
- Current medications
- Adverse event assessment

Long-term/Outcomes Follow-Up Procedures

As standard of care, patients will be followed by oncology provider(s) at least annually after surgery (+/- 3 months). Cancer recurrence outcomes up to five years post-treatment will be collected by chart review annually.

VI. ADVERSE EVENTS: DEFINITIONS AND REPORTING REQUIREMENTS

Adverse Event (AE) and Serious Adverse Events (SAE)

The investigator and team will follow the Medical College of Wisconsin policies related to adverse event reporting. Common Terminology Criteria for Adverse Events (CTCAE) version 5 would be used. This information may be found on the [Human Research Protection Program website](#).

Serious AE (SAE) means any untoward medical occurrence:

- **Death.** Results in death.
- **Life threatening.** Is life threatening (refers to an AE in which the patient was at risk of death at the time of the event; it does not refer to an event which hypothetically might have caused death if it were more severe).
- **Hospitalization.** Requires inpatient hospitalization or prolongation of an existing hospitalization
- **Disability/incapacity.** Results in persistent or significant disability or incapacity. (Disability is defined as a substantial disruption of a person's ability to conduct normal life functions).

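### The only scheduled pregnancy test is timed to enrollment, not to first dose, so a premenopausal patient with a delayed start may be dosed on a negative result 28 days old, or at most 56

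*Combined protocol and SAP*

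**What the plan says.** The Study Calendar marks the pregnancy test once, in the Screening column, and footnote 7 restricts it to premenopausal women. The Week 1 column repeats the history, examination, vital signs and performance status, but not the pregnancy test. The test has no mark at surgery or at the end-of-treatment visit either.

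Footnote 2, which is attached to both the Screening and the Week 1 column headings, reads "Screening procedures and drug administration to be done within 28 days of enrollment". Section V gives the same number of days for screening alone: "Screening assessments must be performed within 28 days prior to enrollment", and again, under Screening Assessments, "proceed with the screening procedures and assessments which must be completed within 28 days of prior to enrollment". The list that follows includes "Serum or urine pregnancy test for premenopausal women" with no window of its own. Inclusion item 16 asks for a negative test and gives no time limit.

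Dosing comes after enrollment: "Once enrolled, patients would be treated with the current standard-of-care endocrine therapy" (Section IV, Treatment Plan, item 7). A same-day start is allowed but not required. Footnote 1 says "A patient can be screened and have status of week one on the same day", and Section V (Study Procedures during Treatment) says "The clinic visit can be the same for screening, eligibility assessment and if enrolled, to start treatment with endocrine therapy for week 1". The same paragraph adds "Patients must have met eligibility criteria on Day 1 to be treated".

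**The concern.** Pregnancy is an exclusion (Exclusion item 6), and premenopausal women are part of the stated population. How well the exclusion protects them depends partly on how recent the only scheduled test is when the drug is started. The plan anchors that test on enrollment, so its age at first dose is limited only indirectly, by adding up windows that were written for other purposes.

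Contraception is advised rather than required (Inclusion item 15). Section V plans no further clinic visits during treatment, and the calendar has no later pregnancy test. A pregnancy that begins between the test and the first dose would therefore meet no later scheduled test during the three to five weeks of treatment. What is at stake is the safety of a subgroup: premenopausal patients whose first dose falls on a later day than their screening.

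**Working it through.** The plan states no interval from test to first dose, so there is no figure to reproduce. The permitted maximum follows from the windows.

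**Inputs**
- Test to enrollment: at most 28 days (Section V, stated twice; footnote 2).
- Enrollment to first dose: not negative, because treatment follows enrollment (Treatment Plan, item 7). The upper limit depends on how footnote 2 is read.
- Same-day screening and start: permitted (footnote 1; Section V).

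**Formula**
Maximum test age at first dose = (maximum days from test to enrollment) + (maximum days from enrollment to first dose).

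**Results**
- Same-day start: 0 + 0 = 0 days.
- Footnote 2 as one shared window for screening and dosing: 28 days in total.
- Footnote 2 as two windows, one before and one after enrollment: 28 + 28 = 56 days.

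The 28-day figure does not need footnote 2. Under Section V alone, a patient tested 28 days before enrollment and dosed on the day of enrollment has a test age of 28 + 0 = 28 days. The 56-day figure needs the two-window reading and both extremes in the same patient.

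**Effect of a direct limit before first dose**
- 7 days: the maximum falls by 28 − 7 = 21 days (shared window) or 56 − 7 = 49 days (two windows).
- 14 days: it falls by 28 − 14 = 14 days or 56 − 14 = 42 days.

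**Do the existing safeguards set a test age?**
- *Day 1 eligibility.* The criteria must have been met on Day 1, and they include a negative test. That criterion carries no date, so as written a result 28 or 56 days old satisfies it. No Day 1 test is listed.
- *Week 1 history and examination.* These can raise suspicion of pregnancy, but they are not a test and do not prompt one in the text.
- *Menstrual-status review* (Treatment Plan, item 7). Its stated purpose is the choice of drug, and it is not dated to Day 1.

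**The case against.** The strongest reply is that a control on Day 1 already exists. Eligibility must hold on that day, and pregnant women are ineligible, so a woman known to be pregnant may not be treated however old her test is. The delayed-start patient, the only one at issue, also has a Week 1 history and examination. She must have met a medical oncologist before entry (Treatment Plan, item 5), and the review of menstrual status is described among the steps after enrollment. All of this stands, and it lowers the practical risk. It does not tell the site to retest, nor how recent the result must be.

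The second reply is that footnote 2 is a single sentence with a single 28-day figure, and no other section gives a separate 28-day dosing window after enrollment. This also stands, so 56 days is an upper bound on one reading and not the headline. The two-window reading is still open: the footnote marks both columns, screening precedes enrollment and dosing follows it.

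Third, the documents set no standard for test age that the plan breaches, and the workflow they describe includes a single visit with a gap of 0 days. That is correct. The single visit is optional, however, and the point concerns only patients who do not use it.

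**Conclusion.** The point holds in a limited form. The timing rule permits a negative pregnancy test that is 28 days old at first dose, or at most 56 days old if footnote 2 is read as two windows, for a premenopausal patient who does not start on the screening day. The existing safeguards reduce the risk without setting a test age.

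A reader might infer three stronger things that the documents do not support. The first is that the plan lets pregnant women be treated: the exclusion and the Day 1 rule forbid it, and only the means of verification is loose. The second is that tests will commonly be 56 days old: that figure is a permitted extreme, and the documents give neither the usual delay from screening to dosing nor the number of premenopausal patients, so the number affected is unknown. The third is that the results are compromised: the primary endpoint, sample size and analysis are unaffected.

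The conclusion rests on reading the windows as written. Any specific limit, such as 7 or 14 days, is an assumption, because the documents supply none. This is a cheap safety improvement and not a flaw in the design.

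**What to change.** In the calendar (the pregnancy-test row and footnote 7), in Inclusion item 16 and in Section V, require a negative serum or urine pregnancy test within 7 days before first dose for premenopausal women. The 7 days is an assumption, and the sponsor may choose up to 14. Time the existing screening test to meet the limit where possible. If it is older, repeat it at the existing Week 1 visit and have the result before dosing.

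Reword footnote 2 so that it gives the screening window before enrollment and the drug-start window after enrollment as two separate statements. This removes the ambiguity between 28 and 56 days. The calendar already sets procedure-specific windows for imaging and the lipid panel (footnotes 3 and 6), so the addition fits its form.

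The cost is a change of wording and an occasional repeat test, with its result awaited, for premenopausal patients with a delayed start. No visit is added, and patients who start on the screening day are unaffected.
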